The lack of safe and effective pharmacological treatments for MA use disorders is a critical barrier to improved treatment outcomes. This proposal builds on the published translational findings of reduced PCr[22] and NAA [34, 124] levels in MA use disorders, and the clinical and neuroimaging findings from our preliminary study of creatine for MA-using females. At the same time, it follows the recommendation of experts – including NIDA Director [name] and the eminent substance abuse researcher [name] – that strategies outside the brain dopamine reward system be adopted [56, 125, 126]. Achievement of these *Specific Aims* would validate the notion of neuroprotective agents as potential treatments for MA addiction [15], and in particular those which are also capable of improving mood/anxiety and cognitive symptoms. Incorporating pre- and post-treatment imaging into studies of substance misuse can facilitate identification of the neural predictors and correlates of effective MA treatment [127]. Because the effects of drug use on brain function impede patients' ability to benefit from treatment, studies of drug-related alterations in neurobiology utilizing translational study designs are warranted [127]. Thus, we propose an 8-week, randomized, placebo-controlled trial of creatine for females with MA addiction.

Specific Aims for this proposal are: **1. To define the extent of restoration in bioenergetic dysfunction and neuronal viability following creatine supplementation in female MA users.** We hypothesize that creatine will be superior to placebo in the degree of improvement in PCr and NAA levels, measured with ^{31}P -MRS and ^1H -MRS. Changes to the glutamine/glutamate ratio and GABA will be assessed in an exploratory manner. **2. To assess creatine's antidepressant/anxiolytic effect in female MA users.** We hypothesize that creatine will be

superior to placebo in reducing Hamilton Depression Rating Scale (HAMD) and Beck Anxiety Inventory [97] scores. 3. To Measure the Degree of Cognitive Improvement Associated with Creatine in Female MA Users. We hypothesize that creatine will be associated with greater improvement in cognitive function tests, compared with placebo. In addition to these Specific Aims, we will examine urine drug testing results in an exploratory manner, to determine whether creatine vs. placebo is associated with a greater number of MA-free tests

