Overall Analytic Strategy: The analyses proposed are generalized estimating equations (GEE) regression modeling, which will be used for our longitudinal data analyses with group comparison across treatment visits for the variables of metabolite levels, depression/anxiety symptoms, and cognitive tests. GEE allows robust estimations of standard errors and permits adjustment for time-varying covariates. We assume that measurements made closer in time are more correlated than those made farther apart. Thus, first-order autoregressive structure is assumed. For our repeated measurement data, GEE fits a population-averaged model with working correlation structure to statistically evaluate the time effect of creatine supplementation. We will control for age, other drug abuse, anxiety scores, and tissue partial volume effects in each GEE model. Sidak multiple comparison procedure will be employed to adjust for family wise error (FWE) rate. The Sidak tests make conservative controls of FWE, giving slightly smaller adjusted p-values than the Bonferroni correction.

Overall Power and Sample Size Calculations: For this pilot study, considering a 20% attrition rate, 95 participants will be recruited to achieve a sample size of 75. To determine the minimum effect that would likely be detected with a sample size of 75, a power analysis was performed. Effect for the power analysis was specified as average baseline (over two measures) HAM-D scores compared with average HAM-D scores during active treatment (over eight measures). A gradual onset of effect during active treatment is assumed, starting with an effect of 0 and ending with an effect of 0.5, resulting in an average effect during treatment of 0.25. The effect to be tested was treated as a linear combination of the separate measures (y^*), and a pattern of correlation of 0.5 was used. This generated a standard deviation [105] for y^* that will be different from the within-occasion SD for Y itself. Then the effect magnitude specified was divided by the $SD(y^*)$ to generate an "effective" or de facto effect size, which resulted in an effect size of 1.09 with a power of 0.87.

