Statistical Analysis for Specific Aim 3: Cognitive testing data with a repeated measures design will evaluate the cognitive improvement after 8 weeks of creatine supplementation, specifically in executive and working memory deficits, found in MA users. The relative improvements on WCST, Stroop and WMS-IV scores associated with creatine versus placebo will be tested conservatively with the assumption of independence among comparisons. Independent variables include a time variable of "visit" (baseline and 8 weeks of treatment), creatine" (placebo or creatine group), and an interaction term, "creatine \times visit", where a significant interaction will indicate significant differences between treatments. The depression effect will be

tested by stratifying depressed and non-depressed MA users. Power and Sample Size Calculations: Previous reports, meta-analysis, and our preliminary data suggest that the cognitive deficits of MA users have medium-to-large (0.5 to 0.8) effect size, especially in the episodic memory, compared to healthy subjects. Thus, the proposed sample size (n=76) will have enough power (> 80%) based on Cohen's guidelines with adjusted Sidak p-values of 0.0169. [137, 138]

ADMINISTRATIVE RESPONSIBILITIES

Resources:

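### The Sidak adjustment for the three Aim 3 cognitive tests reads as single-step at 0.0169; this is valid, but a step-down Sidak gives more power at the same 5% familywise error

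*Combined protocol and SAP*

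**What the plan says.** The Overall Analytic Strategy states that a "Sidak multiple comparison procedure will be employed to adjust for family wise error (FWE) rate". It describes the method only by comparison with Bonferroni: "The Sidak tests make conservative controls of FWE, giving slightly smaller adjusted p-values than the Bonferroni correction".

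The statistical analysis section for Specific Aim 3 names the outcomes, "The relative improvements on WCST, Stroop and WMS-IV scores", and says that they "will be tested conservatively with the assumption of independence among comparisons". Its power paragraph claims more than 80% power with n=76 at "adjusted Sidak p-values of 0.0169".

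The plan does not use the terms single-step or step-down. It gives no ordering, gatekeeping or other sequential rule, and it specifies no simultaneous confidence intervals.

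**The concern.** Single-step Sidak holds every test in the family to the strictest level, even after another test in the family has been rejected. Step-down Sidak relaxes the level for the hypotheses that remain, with no increase in the 5% familywise bound. If the plan means single-step, it gives up power on the second and third cognitive tests. Those tests matter if the sponsor wants to report an effect in more than one cognitive domain. The Aim 3 hypothesis is worded broadly: "We hypothesize that creatine will be associated with greater improvement in cognitive function tests, compared with placebo".

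**Working it through.** **Inputs from the plan.** Three tests (WCST, Stroop, WMS-IV); level 0.0169; n=76; 1:1 allocation, so 38 per arm; independence among comparisons.

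**Assumptions not in the plan.** Familywise level 0.05 (implied by 0.0169); two-sided tests; a two-sample t comparison as a simple stand-in for the GEE interaction test; correlation 0.3 between test statistics, with 0 and 0.5 also tried; the same standardised treatment effect d on all three tests unless stated otherwise.

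**The plan's own level.** Single-step Sidak for three tests is 1 − (1 − 0.05)^(1/3) = 0.01695, which is 0.0169 when cut to four decimals. Cutting down is the safe direction: 1 − (1 − 0.0169)^3 = 0.0498, whereas 0.0170 would give 0.0501. Bonferroni would be 0.05/3 = 0.0167, so the plan's comparison with Bonferroni fits ordinary single-step Sidak.

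**Step-down levels.** Order the p-values from smallest to largest. With k hypotheses still untested, use 1 − 0.95^(1/k), and stop at the first failure:

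- k=3: 0.0169, in the plan's rounding
- k=2: 1 − 0.95^(1/2) = 0.0253
- k=1: 0.05

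The first level is the single-step level and the later ones are looser, so every single-step rejection is kept.

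**Power per test, single-step.** The noncentrality is d × √(38/2) = 4.359d, with 74 degrees of freedom and critical value 2.444 at two-sided 0.0169. The exact noncentral t gives 0.849 at d=0.8, 0.401 at d=0.5 and 0.134 at d=0.3.

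**Single-step against step-down.** Simulation, 200,000 draws per scenario, correlation 0.3:

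| Effect on all three tests | Per test, single-step | Per test, step-down | All three, single-step | All three, step-down |
|---|---|---|---|---|
| 0.8 | 0.85 | 0.91 | 0.66 | 0.82 |
| 0.5 | 0.40 | 0.47 | 0.12 | 0.25 |
| 0.3 | 0.13 | 0.15 | 0.01 | 0.04 |

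- *Sensitivity to correlation.* At d=0.8, power for all three goes from 0.61 to 0.80 at correlation 0, and from 0.69 to 0.83 at correlation 0.5.
- *At least one rejection.* This is identical under the two procedures: at correlation 0.3, 0.98 at d=0.8 and 0.71 at d=0.5.
- *Only one real effect.* With d=0.8 on one test and none on the other two, power for that test is 0.85 under both.
- *Rejections lost.* In no draw did single-step reject a hypothesis that step-down did not.
- *Familywise error.* Step-down stayed at or below 0.050, within simulation error, in the global-null and mixed scenarios.
- *Use of the error allowance.* With d=0.8 on two tests and none on the third, the null test is falsely rejected about 0.017 of the time under single-step and about 0.044 under step-down. Both are within 5%.

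**The case against.** Single-step Sidak is a legitimate familywise procedure, and the plan openly calls its approach conservative. Nothing here is contradictory or biased. This stands: the point concerns efficiency only, and a reader who inferred that the planned adjustment is wrong would be mistaken.

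A reader might also infer that the power is given up for no return. That goes too far. Single-step offers simple matching simultaneous intervals and uses less of the error allowance when some effects are real, as the 0.017 against 0.044 comparison shows. The first of these counts for little here, because the plan specifies no such intervals.

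The gain depends on the treatment effects, and the plan gives none for Aim 3. Its range, "cognitive deficits of MA users have medium-to-large (0.5 to 0.8) effect size", is a deficit against healthy subjects, not a creatine-versus-placebo difference. At a treatment effect of 0.3 the gain is about two points per test. Nor does the plan make success in Aim 3 depend on more than one test.

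It is tempting to extend the point to Aims 1 and 2, which each name two outcomes. The documents do not support a figure there: they define no family for those aims and state no two-test level.

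Finally, single-step is an inference. The value 0.0169 appears in a power statement and is also the first step-down level. The description relative to Bonferroni and the absence of any sequential rule make single-step the natural reading. If the sponsor meant step-down, the text still needs to say so.

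**Conclusion.** The point holds as an inexpensive improvement, not as the correction of an error. For Aim 3 with 38 per arm, step-down Sidak adds about 6 to 7 points of power per test if effects of 0.8 or 0.5 are present on all three tests, and about 2 points at 0.3. Power for all three together rises by about 16, 13 and 3 points respectively. These figures rest on two-sided tests, an assumed correlation of 0.3 and assumed equal effects.

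The change does not raise the chance of at least one significant test, and it gains almost nothing if only one effect is real. A reader might infer that it rescues the claim of more than 80% power across the stated 0.5 to 0.8 range. It does not: at 0.5, power per test reaches only 0.47.

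**What to change.** Before the blind is broken, name the step-down (Holm-Sidak) procedure in the Overall Analytic Strategy in place of the unqualified Sidak procedure. For Aim 3, state the levels as 0.0169 for the smallest p-value, 0.0253 for the next and 0.05 for the largest, stopping at the first failure. Use the same procedure for any other family that the sponsor defines; with two tests the levels are 0.0253 and then 0.05.

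The cost is one sentence, with no change to sample size, data collection or conduct. The downsides are that matching simultaneous confidence intervals become less simple and that more of the 5% allowance is used when some effects are real. If unadjusted 95% intervals are reported beside the adjusted p-values, label them as unadjusted, because they can disagree with the adjusted decisions.

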At the screening visit, an ECG will be conducted in order to examine the heart and ensure participant safety; an adult cardiologist will also evaluate all individuals during the screening phase. If during the MRI/MRS scans we unexpectedly discover something that warrants further inspection, we will refer the participant to her primary care provider for follow-up, along with the MRI/MRS report that shows the findings. Any costs related to following up on unexpected findings will be the responsibility of her and/or her insurance provider. In conjunction with the brain scans performed pre- and post-treatment, a brief battery of cognitive tests will be administered, to evaluate change associated with creatine or placebo. Trained psychometricians administer tests on the day of scanning. Scoring is done blind to subjects' group status, clinical ratings and imaging results. The cognitive testing battery instruments were

chosen because they are sensitive to frontal lobe integrity: the Wisconsin Card Sorting Task (WCST)[129], the Stroop Color-Word Test[130, 131], and the Wechsler Memory Scale (WMS-IV)[132]. Furthermore, the WCST[133], Stroop Test[134] and WMS-IV [90] each have been associated with performance deficits in MA users.

TABLE 2A Schedule of Procedures for Methamphetamine-dependent Females												
	Screening	Treatment Phase								Follow Up Phase		
Study Week →	-2 to 0^a	1*	2*	3*	4*	5*	6*	7*	8*	9	10	11
Informed Consent, Demographics	X											
Medical History & Physical Exam, ECG	X											
Hematology & Chemistries	X									X		
Phlebotomy for Creatinine Levels	X				X					X		
HIV	X											
Pregnancy Test and vital signs	X	X	X	X	X	X	X	X	X	X	X	X
PRISM Diagnostic Interview	X											
ASI	X									X		
Randomization to Creatine or Placebo	X											
Treatment with Creatine or Placebo		X	X	X	X	X	X	X	X			
Urine Drug Screen / Other Drug Use	X	X	X	X	X	X	X	X	X	X	X	X
Concomitant Medications	X	X	X	X	X	X	X	X	X	X	X	X
Food Frequency Questionnaire	X									X		
Cognitive Tests: WCST, STROOP and WMS-IV (with WASI vocabulary)***	X									X		
Adverse Events		X	X	X	X	X	X	X	X	X	X	X
Treatment Program Attendance	X	X	X	X	X	X	X	X	X	X	X	X
Clinical Scales: HAMD**, BAI**, CGI-S**, C-SSRS	X	X	X	X	X	X	X	X	X	X	X	X

³¹ P-MRS and ¹ H-MRS****	X									X		
*During the 8 Treatment Weeks, MA Subjects Have 2 Study Visits Per Week (separated by \geq 48 hours)												
**Procedure will be collected at one of the twice weekly visits												

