***MA subjects with difficulty scheduling the cognitive testing appointment may be allowed to omit these measures and continue in the study as to not delay treatment and in order to facilitate timely enrollment, which is critical for this population.												
****If an individual is screened and determined to be a good fit for study participation but also has a contraindication to MRI scanning, the principal investigator may allow them into the study, however, they will not be scanned for their safety.												
CGI-S = Clinical Global Impressions-Severity Depression Score; C-SSRS = Columbia-Suicide Severity Rating Scale; HAMD = Hamilton Rating Scale for Depression; BAI = Beck Anxiety Inventory; PRISM = Psychiatric Research Interview for Substance and Mental Disorders; STROOP = Stroop Color Word Test; WCST = Wisconsin Card Sorting Test; WMS-IV = Wechsler Memory Scale; WASI = Wechsler Abbreviated Scale of Intelligence; ASI = Addiction Severity Index.												
^a Screening may happen over the course of 2-3 visits.												

TABLE 2B Schedule of Procedures for Healthy Controls

	Screening									Final Visit
Study Week →	-1 to 0 ^a	1	2	3	4	5	6	7	8	9
Informed Consent, Demographics	X									
Medical History & Physical Exam, ECG	X									
Hematology & Chemistries	X									
Phlebotomy for Creatinine Levels	X									
HIV	X									
Pregnancy Test	X									X
PRISM Diagnostic Interview	X									
Food Frequency Questionnaire	X									X
Urine Drug Screen / Other Drug Use	X									X
Concomitant Medications	X									X
Vital Signs	X									X
Cognitive Tests: WCST, STROOP and WMS-IV (with WASI vocabulary)	X									X
Treatment Program Attendance	X									X
Clinical Scales: HAMD**, BAI**, CGI-S**, C-SSRS	X									X

³¹ P-MRS and ¹ H-MRS	X									X
CGI-S = Clinical Global Impressions-Severity Depression Score; C-SSRS = Columbia-Suicide Severity Rating Scale; HAMD = Hamilton Rating Scale for Depression; BAI = Beck Anxiety Inventory; PRISM = Psychiatric Research Interview for Substance and Mental Disorders; STROOP = Stroop ColorWord Test; WCST = Wisconsin Card Sorting Test; WMS-IV = Wechsler Memory Scale; WASI = Wechsler Abbreviated Scale of Intelligence.										
^a Screening may happen over the course of 2-3 visits.										

RISKS AND BENEFITS TO STUDY PARTICIPANTS

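### The HAMD power calculation averages two baseline ratings, but the visit schedule commits to only one

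*Combined protocol and SAP*

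**What the plan says.** Overall Power and Sample Size Calculations compares "average baseline (over two measures) HAM-D scores" with "average HAM-D scores during active treatment (over eight measures". The effect is assumed to grow from 0 to 0.5, "resulting in an average effect during treatment of 0.25", and "a pattern of correlation of 0.5 was used". The section reports a de facto effect size of 1.09 and a power of 0.87 for 75 participants, and gives no alpha or sidedness.

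In Table 2A, the row "Clinical Scales: HAMD, BAI, CGI-S, C-SSRS" has one mark under the single screening column (weeks -2 to 0), one in each of treatment weeks 1 to 8, and one in each of follow-up weeks 9 to 11. A table note limits HAMD to one of the two weekly treatment visits, so the eight treatment ratings agree with the power text. Footnote a adds: "Screening may happen over the course of 2-3 visits".

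Overall Analytic Strategy describes GEE models for "longitudinal data analyses with group comparison across treatment visits", in which "first-order autoregressive structure is assumed". It does not name the powered contrast of baseline mean against treatment mean as the analysis, and its covariate list does not include baseline HAMD.

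**The concern.** The power text needs ten HAMD ratings by the end of treatment, two before and eight during. The schedule marks nine. The eight treatment ratings are accounted for, so the gap is at baseline.

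This matters because HAMD is the outcome on which the overall sample size rests, and it is also an Aim 2 outcome. In a change contrast with eight treatment ratings and only one or two baseline ratings, the baseline average can contribute most of the variance, so a missing baseline rating may cost more than a missing treatment rating.

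The documents also leave open which HAMD score counts as baseline. Table 1 uses a current HAMD score for entry and a change from baseline in its early-termination criteria. The sections should be reconciled on that definition.

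**Working it through.** **Inputs from the plan.** Two baseline and eight treatment ratings; average effect 0.25; correlation 0.5; 75 completers (all from Overall Power and Sample Size Calculations); 1:1 allocation and 123 randomised (Design).

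**Assumptions.** Effects are in units of the within-occasion SD. The correlation of 0.5 is exchangeable unless stated otherwise. The test is two-sided at 5%. Power is from the noncentral t with arms of 37 and 38.

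**1. The plan's own figure.** Let y* be the mean of eight treatment ratings minus the mean of b baseline ratings. With exchangeable correlation ρ,

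Var(y*) = (1 − ρ)(1/b + 1/8).

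For b = 2 and ρ = 0.5: 0.5 × 0.625 = 0.3125, SD = 0.559, de facto effect = 0.25/0.559 = 0.447. This is not 1.09, which would need ρ of about 0.92. The printed pair is also inconsistent internally. An effect of 1.09 with 75 participants in two arms gives power above 0.99, while power of 0.87 corresponds to an effect of about 0.71. The effect of one baseline must therefore be measured from the recomputed two-baseline value.

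**2. One baseline instead of two, for the powered contrast.** For b = 1: 0.5 × 1.125 = 0.5625, SD = 0.750, de facto effect = 0.25/0.750 = 0.333.

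| Baselines | SD(y*) | Effect | Power, 75 | Power, 98 |
|---|---|---|---|---|
| 2 | 0.559 | 0.447 | 0.48 | 0.59 |
| 1 | 0.750 | 0.333 | 0.30 | 0.37 |

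The last column uses 123 × 0.8 = 98.4, that is, the randomised number in Design with the plan's 20% attrition.

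The variance ratio is 0.5625/0.3125 = 1.8, so SD rises by 34%. The factor (1 − ρ) cancels, so the ratio is the same for any exchangeable correlation. Power at 75 falls from 0.37 to 0.23 at ρ = 0.3, and from 0.86 to 0.61 at ρ = 0.8.

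**3. Other analyses, including AR(1).** The change variance is Var(B) + Var(T) − 2Cov(B,T), where B and T are the baseline and treatment means. With baseline adjustment the residual variance is Var(T) − Cov(B,T)²/Var(B). AR(1) is taken as the true correlation, with equally spaced ratings.

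- AR(1) with 0.5, Var(T) = 0.3127. Two baselines: Var(B) = 0.75, Cov = 0.0934. One baseline: Var(B) = 1, Cov = 0.1245.
  - Change: 0.8760 (SD 0.936) against 1.0637 (SD 1.031).
  - Adjusted: 0.3011 (SD 0.549) against 0.2972 (SD 0.545).
- Exchangeable with 0.5, Var(T) = 0.5625, Cov = 0.5.
  - Adjusted: 0.5625 − 0.25/0.75 = 0.2292 (SD 0.479) against 0.5625 − 0.25 = 0.3125 (SD 0.559).

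| Analysis | SD, 2 baselines | SD, 1 baseline | Change in SD | Power at 75, 2 to 1 |
|---|---|---|---|---|
| Exchangeable, change | 0.559 | 0.750 | +34% | 0.48 to 0.30 |
| Exchangeable, adjusted | 0.479 | 0.559 | +17% | 0.61 to 0.48 |
| AR(1), change | 0.936 | 1.031 | +10% | 0.21 to 0.18 |
| AR(1), adjusted | 0.549 | 0.545 | about 0 | about 0.50 in both |

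**The case against.** **The table may not be counting ratings.** A mark in a column that covers two weeks and up to three visits may only show that the procedure occurs in that period. No section says HAMD is rated only once before treatment. This stands: a second rating is possible. A reader might infer that the schedule fixes baseline at a single score, and the documents do not go that far. But the footnote repeats no procedure, and the same column carries single marks for consent, the HIV test and randomisation. A rating that is only possible is not one on which a power statement can rest.

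**Ten ratings can be found.** Screening plus weeks 1 to 9 makes ten. The second scan follows eight weeks of treatment and is marked at week 9, so week 9 could be the last treatment rating and a pre-dose week 1 rating could be the second baseline. The documents do not say this, and Table 2A marks treatment in weeks 1 to 8 and places week 9 in follow-up.

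**The powered contrast is not the planned analysis.** This stands, and it limits the point. A reader might infer that the trial's analysis will carry 80% more variance. That holds only for an unadjusted change contrast with exchangeable correlation, whereas the plan is a GEE with an AR(1) structure.

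**The fall from 0.48 to 0.30 does not start from the stated 0.87.** This is also correct. A reader might infer that a missing baseline takes power from 0.87 to 0.30. Most of that gap is the separate failure of the printed figures to reproduce. If 0.87 is taken at face value and only SD(y*) is rescaled, power is about 0.63.

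**Conclusion.** The point holds as a mismatch between the power calculation and the schedule. The calculation averages two baseline HAMD ratings, the schedule commits to one, and nothing defines where a second would come from.

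For the contrast that was powered, one baseline raises SD by 34% and lowers power by about 18 percentage points at 75 completers (22 points at 98). In the other analyses examined, the rise in SD runs from 17% down to nothing, and under AR(1) it is at most about 10%. The documents do not establish a large loss of precision in the planned analysis.

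These sizes rest on a two-sided 5% test, unit within-occasion SD, near-equal arms, and reading the stated 0.5 as exchangeable or AR(1) as labelled. The mismatch itself rests on none of these. It is separate from the irreproducible 1.09 and 0.87: correcting that arithmetic alone would still leave the number of baseline ratings unsupported by the schedule.

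**What to change.** Choose one of two changes.

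- Mark HAMD at two named screening visits before randomisation in Table 2A, and define the analysis baseline as their mean. The cost is one more interview, at a visit that may already occur.
- Keep a single baseline rating and restate the power for it. The cost is a less favourable figure under most of the analyses above.

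In either case, recompute the power for the GEE comparison that will be run. State alpha, sidedness, the correlation structure, whether baseline HAMD is adjusted for, and the number of completers. Also state which HAMD score is baseline, and reconcile the sections that refer to it. Apart from the possible extra interview, these are edits to the text and table.

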In addition to these **Specific Aims**, we will monitor subjects' MA use, as improvements in brain bioenergetics, mood/anxiety and may decrease MA usage. Therefore, we will record urine drug testing results, to determine whether creatine vs. placebo is associated with a greater number of MA-free tests during the 8 weeks of randomized treatment.

PARTICIPANT SELECTION CRITERIA

123 women will be randomly assigned in a 1:1 ratio to either creatine or placebo for eight weeks. Table 1 outlines eligibility criteria.

TABLE 1 INCLUSION AND EXCLUSION CRITERIA

INCLUSION CRITERIA:

- Female gender, ages 18-55 inclusive
- Current primary diagnosis of MA dependence or abuse, with MA preferred drug of abuse (Lifetime MA use > 20 grams)
- Current diagnosis of Major Depressive Disorder (MDD)
- Current HAMD score ≥ 10
- Clinical Global Impressions–Severity (CGI-S) depression score ≥ 4
- If taking a psychotropic medication for depressed mood, regimen must be stable for ≥ 4 weeks prior to randomization

EXCLUSION CRITERIA:

- Persons unable to provide adequate informed consent
- Persons who are at clinically significant suicidal or homicidal risk
- Primary substance-related diagnosis *other than* MA dependence or abuse
- Comorbid substance dependence diagnosis, other than nicotine (substance abuse diagnoses are not excluded)
- Positive pregnancy test, due to the unknown effects of MRI scanning on the unborn fetus
- Positive test for antibody to the Human Immunodeficiency Virus (HIV)
- History of renal disease
- Clinically significant medical or neurological illness identified by history, physical exam and laboratory testing
- Known or suspected intellectual disability, or developmental disorder, e.g. autism
- History of hypersensitivity reaction to creatine

WITHDRAWAL / EARLY TERMINATION CRITERIA:

- Withdrawal of informed consent
- Suicide attempt
- Psychiatric hospitalization
- Onset of bipolar disorder or psychotic disorder
- Positive pregnancy test
- Incarceration
- Inability to comply with study protocol

▪ Treatment with electroconvulsive therapy (ECT)▪ Increase in HAMD score > 25% from baseline▪ Serious adverse event

▪ HEALTHY CONTROL SUBJECTS:
 
▪ Female gender, ages 18-55 inclusive▪ No current or past DSM-5 diagnosis, as determined by clinical and structured interviews▪ No first-degree relatives with known or suspected DSM-5 diagnosis

DESIGN

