The proposed study will use a randomized, double-blind, placebo-controlled design. 123 participants will be randomly assigned in a 1:1 ratio to placebo or 5 grams of daily creatine treatment for eight weeks. We also plan to recruit 24 age-matched females (18-55).

STUDY PROCEDURES

All procedures performed by study personnel are research-related. None of the study activities will be considered standard of care. There will be no cost to study subjects for their participation. Participants will be compensated for their time and travel. Table 2A and 2B outlines the schedule of study procedures for treated participants and healthy controls.

Consent will be obtained before any study procedures are initiated. Potential participants will be informed of the study and offered a consent form to review. They will be encouraged to discuss study participation with their relatives. If a potential participant expresses interest in study participation, the informed consent process will be conducted. After the informed consent process, individuals will be offered time to consider study participation and to ask questions. Subjects and parents/guardians will have the opportunity to discuss the study with a study team member in a setting free of coercion. The language of the informed consent form is written at a level easily understood by the subject and any questions asked by the subject will be answered honestly and free of bias. A specific meeting time will be set up between a study team member and the participant where the entire informed consent document will be carefully explained in its entirety. The length of the meeting will be designed so there is the necessary amount of time for all questions to be answered.

Randomization of participants to the two treatment conditions will take place according to a randomization list generated prior to the start of recruitment. 47 (50%) will be randomized to placebo. The study will be conducted as a double-blind trial, with neither participants nor research staff aware of participant assignment. Except in cases of medical emergency, the double-blind will not be "broken" until recruitment is closed and the final participant has completed 8 weeks of treatment with investigational drug. There is no "washout period" for any participant in this study, and participants randomized to placebo will continue treatment with a psychotropic medication throughout their time in the study.

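### The HAMD effect size of 1.09 and power of 0.87 do not follow from the stated inputs and contradict each other; the inputs give an effective size near 0.45 and power near 0.48 with 75 women

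*Combined protocol and SAP*

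**What the plan says.** The section Overall Power and Sample Size Calculations plans to recruit 95 women so that 75 remain after 20% attrition. Its stated purpose is "To determine the minimum effect that would likely be detected with a sample size of 75". The quantity powered is "average baseline (over two measures) HAM-D scores compared with average HAM-D scores during active treatment (over eight measures". The effect rises gradually from 0 to 0.5 during treatment, "resulting in an average effect during treatment of 0.25", and "a pattern of correlation of 0.5 was used". The effect is then divided by the SD of this linear combination, y*, "which resulted in an effect size of 1.09 with a power of 0.87".

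The section does not give the value of SD(y*), the alpha, the sidedness or the unit of the effect. It also does not say whether the test is within or between arms.

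Aim 2 hypothesises that creatine will be "superior to placebo in reducing Hamilton Depression Rating Scale (HAMD) and Beck Anxiety Inventory" scores. On numbers, Participant Selection Criteria says "123 women will be randomly assigned in a 1:1 ratio to either creatine or placebo for eight weeks", and Design repeats this ("123 participants will be randomly assigned in a 1:1 ratio to placebo"). Study Procedures puts 47 (50%) on placebo, which implies 94.

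**The concern.** The paragraph prints enough inputs to recompute the effective size, and 1.09 looks far too large for an average effect of 0.25. It would require SD(y*) to be less than a quarter of the within-occasion SD. The pair of outputs is also suspect, since an effect above one SD with 75 women in two arms should give power very close to 1. Finally, the contrast described is baseline against treatment, while Aim 2 compares creatine with placebo.

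Aim 3 has its own justification (n=76), so this is the only power statement for the HAMD hypothesis. A reader told that power is 87% could take a null HAMD result as evidence against an effect that the trial had only about an even chance of detecting. The minimum detectable effect, which the paragraph sets out to give, cannot be recovered from what is printed.

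**Working it through.** **Inputs (power section).** Two baseline and eight treatment scores; average effect 0.25; correlation 0.5; effective size = effect / SD(y*); 75 analysed, taken as 37 and 38 under the 1:1 allocation. *Assumed:* the effect is in within-occasion SD units, the correlation is the same for every pair of visits, and alpha is 0.05.

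**1. Effective size by the stated rule.**
Var(y*) = (1 − 0.5)(1/8 + 1/2) = 0.3125, so SD(y*) = 0.559.
Effective size = 0.25 / 0.559 = **0.447**. The plan prints 1.09.
The final effect in place of the average gives 0.5 / 0.559 = 0.894. To reach 1.09, SD(y*) would have to be 0.25 / 1.09 = 0.229. That needs a common correlation of 1 − 0.229²/0.625 ≈ 0.92, or else an average effect of 1.09 × 0.559 ≈ 0.61.

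**2. Do 1.09 and 0.87 agree?** (noncentral t)
- 1.09 with 37/38: power 0.996 at two-sided 0.05, and 0.987 at 0.0169, the Sidak level given for Aim 3.
- 0.87 at 1.09: about 17 per arm, or about 11 women in a within-arm test.
- 0.87 with 37/38: effective size 0.72, an average effect of 0.722 × 0.559 = 0.40 SD.

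**3. Power for creatine against placebo on mean change.** Analysed N is 75 (37/38), 98 (123 × 0.8 = 98.4; 49/49) or 123 (61/62).

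For adjustment for mean baseline, the variance of the treatment mean is 0.5 + 0.5/8 = 0.5625, that of the baseline mean is 0.5 + 0.5/2 = 0.75, and their covariance is 0.5. The residual variance is 0.5625 − 0.25/0.75 = 0.2292, the SD is 0.479 and the effective size is 0.25 / 0.479 = 0.522.

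| | N=75 | N=98 | N=123 |
|---|---|---|---|
| Unadjusted (0.447), two-sided | 0.48 | 0.59 | 0.69 |
| Unadjusted, one-sided | 0.61 | 0.71 | 0.79 |
| Baseline-adjusted (0.522), two-sided | 0.61 | 0.73 | 0.82 |
| Baseline-adjusted, one-sided | 0.72 | 0.82 | 0.89 |

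The smallest average difference with 80% power (two-sided, unadjusted) is 0.656, 0.572 and 0.509, each × 0.559, which gives 0.37, 0.32 and 0.28 SD. The plan assumes 0.25.

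**4. Other readings.**
- First-order autoregressive correlation of 0.5, the structure named for the GEE models: effective size 0.267, power 0.21 with 75.
- Common correlation from 0.3 to 0.8: effective size 0.38 to 0.71.
- One baseline score: Var(y*) = 0.5(1/8 + 1) = 0.5625, effective size 0.333, power 0.30.
- The most efficient weighting over time, which is not the mean contrast described: effective size 0.837, power 0.947 at alpha 0.05 and 0.878 at 0.0169.
- Within-arm test at 0.447: 0.856 (n=38, one-sided) or 0.851 (n=47, two-sided).

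Some of these come near 0.87. None gives 1.09, and none of those near 0.87 is the mean-change comparison of creatine with placebo in 75 women.

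**The case against.** The strongest reply is that both printed figures can be traced to the plan's inputs. Dividing 0.25 by the baseline-adjusted *variance* gives 0.25 / 0.2292 = 1.09. The matching SD, 0.479, gives an effective size of 0.522, and a within-arm two-sided test with 37 women then has power 0.871. So one variance yields both numbers.

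The arithmetic is right, and it may be how the figures arose, though it could be coincidence. It does not rescue them. The text says the effect was divided by an SD, mentions no baseline adjustment, and serves an aim that compares two arms. On this route 1.09 is not an effect size, and 0.87 is the power of a different test.

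Three further points carry some weight. First, 0.447 depends on reading the correlation as constant; the autoregressive reading lowers it to 0.267. Second, if a baseline-adjusted analysis was intended, 0.522 is the relevant figure. Third, the plan calls the study a pilot and, under Trial Stopping Rules, a feasibility study. That tempers what is expected of its power but does not excuse a wrong figure. The mismatch between 75/95 and 123 is a separate inconsistency and not evidence for the arithmetic error, but it must be settled before power can be restated.

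**Conclusion.** The concern holds and must be fixed. By the plan's own rule the effective size is 0.447, less than half the printed 1.09. The conflict between 1.09 and 0.87 at 75 women does not depend on SD(y*) or the correlation, and no usual alpha or sidedness removes it. On the stated inputs, power for creatine against placebo with 75 women is about 0.48 (two-sided 0.05, unadjusted) or 0.61 (adjusted for mean baseline), not 0.87. If all 123 are analysed it is 0.69 or 0.82.

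These powers rest on the effect being in within-occasion SD units, a constant correlation of 0.5, two baseline scores, alpha 0.05, and a t-test on mean change as a stand-in for the planned GEE model. The figure of 98 assumes that the plan's 20% attrition applies to 123.

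**What to change.** First settle and state the comparison (creatine against placebo), alpha, sidedness, effect unit, correlation structure, number of baseline scores, any baseline adjustment, and an analysed N reconciled with the 123 randomised. Then replace the sentence giving 1.09 and 0.87. If the unadjusted mean contrast is kept, it could read:

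> For the creatine-versus-placebo difference in mean HAMD change (mean of 8 treatment scores minus mean of 2 baseline scores), an average effect of 0.25 within-occasion SD and a constant correlation of 0.5 give SD(y*) = 0.559 and an effective size of 0.447. At [alpha, sidedness] with [N] analysed, power is [x]; the smallest average difference detectable with 80% power is [y] SD.

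At two-sided 0.05, x and y are 0.48 and 0.37 (N=75), 0.59 and 0.32 (N=98), or 0.69 and 0.28 (N=123). If a baseline-adjusted analysis is intended, say so and use SD 0.479, effective size 0.522 and power 0.61, 0.73 or 0.82. If the correlation is meant to be autoregressive, recompute on that basis.

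The cost is a text change once the sponsor has made these decisions. It adds no patients. The stated power becomes less favourable.
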